# Statistical Analysis Plan

Study alias & e-track number(s): ZOSTER-063 (204928)

## 7.1.3.2. SF-36

The SF-36 is a multi-purpose health survey with 36 questions (refer to the website address <http://www.sf-36.org/demos/SF-36.html> for a sample of the questionnaire) [Ware, 2001; SF-36.org, 2014; Error! Reference source not found., 2008; SF-36 sample, 2014]. The concepts underlying the construction of the SF-36™ scales and summary measures incorporates a taxonomy of three levels: (1) 36 items; (2) eight scales (see Table 4 for details); and, (3) two summary measures (Physical Component and Mental Component Scores) that aggregate scales. All but one of the 36 items (self-reported health transition) are used to score the eight SF-36™ scales. Each item is used in scoring only one scale. Scale scores will be constructed following the summated ratings and standardized SF-36™ scoring algorithms. A standardized SAS macro provided by Hays will be used to perform the scoring (<http://gim.med.ucla.edu/FacultyPages/Hays/util.htm>).

The SF-36 health survey questionnaires will be completed by all subjects at each study visits (i.e., Visit 1 Day -7, Visit 2 Month 0 (before the vaccination), Visit 3 Day 7, Visit 4 Month 2 (before the vaccination) and Visit 5 Day 67). Additionally, after each vaccination, the subjects will be given the SF-36 questionnaires to take home and asked to complete only questions 3a through 3j on a daily basis on Days 1 to 6 post-vaccination. Subjects will be asked to return the completed questionnaires at the next visit (Visits 3 and 5). Completed questionnaires are to be collected and the subject responses transcribed into the eCRF.

**Table 4 Construction of The Eight Scales Generated from the SF-36**

Scale	Items	Response Categories Per Item
Physical Functioning (PF)	3a, 3b, 3c, 3d, 3e, 3f, 3g, 3h, 3i, 3j	3
Role Physical (RP)	4a, 4b, 4c, 4d	5
Bodily Pain (BP)	7*, 8*	6, 5
General Health (GH)	1*, 11a, 11b*, 11c, 11d*	5
Vitality (VT)	9a*, 9e*, 9g, 9i	5
Social functioning (SF)	6*, 10	5
Role Emotional (RE)	5a, 5b, 5c	5
Mental Health (MH)	9b, 9c, 9d*, 9f, 9h*	5

\* Item Reversed

## 7.1.3.3. EQ-5D

The EQ-5D questionnaire is a generic measure of health status that provides a simple descriptive profile and a single index value (refer to the website address [http://www.euroqol.org/fileadmin/user\\_upload/Documenten/PDF/Products/Sample\\_UK\\_English\\_for\\_a\\_sample\\_of\\_the\\_questionnaire](http://www.euroqol.org/fileadmin/user_upload/Documenten/PDF/Products/Sample_UK_English_for_a_sample_of_the_questionnaire) [below 1996; EQ-5D,2014; EQ-5D sample, 2014]). The EQ-5D defines health in terms of mobility, self-care, usual activities, pain/discomfort and anxiety/depression. The 5 items are combined to generate health

# Statistical Analysis Plan

Study alias & e-track number(s): ZOSTER-063 (204928)

profiles, i.e. a respondent who responds 1 (no problem\no symptom) to all 5 items has a profile “11111” and similarly a subject who responds with the highest level of difficulty or symptom to all items has a profile “33333”. These profiles are subsequently converted to a continuous single index utility score using a one to one matching, e.g. “11111”=1.00, “22222”=0.52 and “33333”= -0.59, using value sets (i.e. matching profiles to single index utility scores). The US TTO (Time-Trade-Off) value set will be used for the analysis.

The EQ-5D also contains a visual analogue scale (VAS). The VAS records the respondent’s self-rated health on a vertical, visual analogue scale where the endpoints are labelled ‘Best imaginable health state’ and ‘Worst imaginable health state’. The score ranges from 0 to 100, with 100 representing the best imaginable health state and 0 representing the worst imaginable health state. This information can be used as a quantitative measure of health outcome as judged by the individual respondents.

The EQ-5D questionnaires will be completed by all subjects at each study visits (i.e., Visit 1 Day -7, Visit 2 Month 0 (before the vaccination), Visit 3 Day 7, Visit 4 Month 2 (before the vaccination) and Visit 5 Day 67). Additionally, after each vaccination, the subjects will be given the EQ-5D questionnaires to take home and asked to complete the entire EQ-5D questionnaire on a daily basis on Days 1 to 6 post-vaccination. Subjects will be asked to return the completed questionnaires at the next visit (Visits 3 and 5). Completed questionnaires are to be collected and the subject responses transcribed into the e-CRF.

#### 7.1.3.4. Area Under the Curve Calculation (AUC) applied to QALY

The AUC method will be applied to the EQ-5D utility score in order to estimate the QALY loss over the 7 days (day 1 to day 7) post dose 1 and dose 2. The calculation of AUC will be based on the trapezoidal rule [Yeh, 2002]. The trapezoidal rule is a numerical integration method to be used to approximate integral or area under curve. The QALY loss will be calculated according to the following steps;

##### **Step1**

The baseline or reference value will be calculated from the assessments at day -7 and day 0 for dose 1 and the assessments at day -7, day 0 and day 60 for dose 2. For dose 1 the mean of the two assessments at day -7 and day 0 will be calculated. This value will then be assumed to have been the utility in the 7 days pre vaccination dose 1. Note that if vaccination dose 1 occurred more than 14 days after the scheduled day -7 then the EQ-5D assessment will not be used and the baseline utility score will be based on the value at day 0 only. To summarise:

Dose 1 : Baseline utility=7\*mean(Day -7 utility, Day 0 utility)

Dose 2 : Baseline utility=7\*mean(Day -7 utility, Day 0 utility, Day 60 Utility)

## Statistical Analysis Plan

GlaxoSmithKline

Study alias & e-track number(s): ZOSTER-063 (204928)

### Step2

The QALY/week for the 7 days post dose is calculated for each subject using the following formula:

$$AUC_{0-7} = \sum_{k=1}^6 (t_{k+1} - t_k) \frac{(y_k + y_{k+1})}{2}$$

Where  $t_k$  is the day of assessment  $k$  relative to vaccination and  $Y_k$  is the utility score on day  $k$  relative to vaccination.

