While grade 3 reactogenicity is defined as preventing ADL, there is no clear understanding available on how this translates to impact on the daily Physical Functioning (PF) of an individual. As such this study is designed to quantify the impact of reactogenicity in terms of PF (e.g., walking, carrying groceries, climbing stairs, etc.). In addition, the Quality-adjusted life year (QALY) loss associated for both *Zostavax*-vaccinated and non-vaccinated subjects with a HZ case that did not lead to PHN, has been estimated to be approximately 0.01 (i.e., 3.65 days) [Pellissier, 2007]. For HZ cases that led to PHN, it was between 38.69 and 56.94 days, resulting in QALY losses of 0.106–0.156 depending on age for non-vaccinated subjects, [Pellissier, 2007]. Similar results were observed in the ZOSTER-006 and ZOSTER-022 studies with the HZ/su vaccine. As such, QALY loss can be avoided by preventing HZ and PHN, through HZ/su vaccination. However reductions in QALY loss by preventing HZ and PHN through HZ/su administration could be partially offset by the QALY loss related to reactogenicity that is associated with vaccination.

In assessing the impact on QoL, the QALY loss due to adverse events is an important parameter to include when calculating the cost/effectiveness of HZ/su compared to no vaccination. These data will be included in models which analyze net QALY loss avoided by preventing HZ and PHN by vaccinating with HZ/su. Furthermore, only limited data are available to assess the impact of the reactogenicity on the Quality of Life (QoL) and PF of individuals exposed to the HZ/su vaccine or vaccination in general. These data are important to both Health Care Providers (HCPs) and policy makers. Additional characterization of the reactogenicity will allow vaccinators to better inform vaccinees before the administration of the vaccine. Therefore, this study will be conducted to enhance our understanding of HZ/su vaccine reactogenicity, and to provide more complete information to vaccinators and persons who will receive the vaccine.

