### 4.2. Secondary endpoints

- Change in mean SF-36 PF scale score.
  - Baseline\* versus mean score over the period day 1 to day 7\*\* after second vaccination.
- Change in mean SF-36 PF single item scores.
  - Baseline\* versus mean score over the period day 1 to day 7\*\* after each vaccination.
- Change in SF-36 Role Physical scores.
  - Baseline\* versus score on day 7\*\* after each vaccination.
- Change in the QALY.
  - Baseline\* versus combined score over the period day 1 to day 7\*\* after each vaccination.
- Healthcare resource utilization (i.e., hospitalization, telephone calls, medical visits and specialist visits, medication intake).
  - Days 0 to 6 after each vaccination.
- Work loss for subjects.
  - Days 0 to 6 after each vaccination.
- Work loss for the non-dedicated caregivers.
  - Days 0 to 6 after each vaccination.
- Extra work for dedicated caregivers.

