### Step3

The QALY Loss is then calculated as the difference between the baseline utility (from step 1) and the AUC value (from step 2).

It is anticipated that the majority of subjects will have daily assessments post dose according to the schedule (i.e. on each of the days 1 to 7) however it is expected that some subjects will be missing daily assessments post dose. In the case of missing assessments between days 1 and 7 the AUC in step 2 will be calculated regardless of the number of assessments post dose. However in the case of the last assessment falling outside of the 7 day window, (for example on day 8), an adjustment will be made before calculating the AUC.

[Figure 1](#) represents the Utility scores for a hypothetical subject. This subject has consecutive assessments on day 5 and day 8 and no assessments on days 6 or 7. Because the AUC must be calculated over a period of 7 days, the day 8 value cannot be included in the formula. However to calculate the AUC, a derived value on day 7 is calculated based on a linear interpolation of the values on days 5 and 8. This derived value on day 7 is then included in the formula given in step 2. The dashed line in the figure represents the linear interpolation between the two assessments either side of day 7.

The calculation of the QALY loss for this hypothetical subject is explained in [Table 5](#).

[figure not shown]

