**Figure 1 Hypothetical Example of utility Scores over Time**

**Table 5 Calculation of QALY for hypothetical Subject in figure 1**

Day	Score	$t_{k+1}-t_k$	$(Y_k+Y_{k+1})/2$	Product
-7	0.89			
0	0.85	1	0.800	0.800
1	0.75	1	0.725	0.725
2	0.70	1	0.710	0.710
3	0.72	1	0.730	0.730
4	0.74	1	0.745	0.745
5	0.75	1	0.765	0.765
7	0.78	2		
8	0.8			
Total				4.475

Note. The value at day 7 is interpolated from the values at day 5 and day 8.

The baseline score is calculated as  $7*(0.89+0.85)/2 = 6.09$

The AUC between days 0 and 7 is 4.475. Hence the QALY loss / week is calculated as 1.534.

The 95% CI for the LSmeans of the QALY loss will be obtained using a multiple regression model. The model will include age strata, gender and frailty status as the fixed effect. The Following Code will implement this model in SAS:

```
ods output lsmeans=lsmeans;
proc mixed data=DATASET;
  class agecat gender frail;
  model qaly=agecat frail gender/ cl;
  lsmeans frail/pdiff cl;
  lsmeans gender/pdiff cl;
  lsmeans agecat/pdiff cl;
quit;
run;
```

The 95% CI for utility scores will be obtained pre- and post-vaccination separately assuming that utility scores were normally distributed with unknown variance.

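### SAP 7.1.3.4 subtracts a six-interval area from a seven-day baseline, which adds about one day of utility to each dose's QALY loss if programmed as written; the worked example is also wrong

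*SAP*

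**What the plan says.** SAP 7.1.3.4 derives QALY loss in three steps.

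- **Step 1** averages the pre-vaccination utilities (day -7 and day 0 for dose 1; day -7, day 0 and day 60 for dose 2) and multiplies by 7. For dose 1 it explains: "This value will then be assumed to have been the utility in the 7 days pre vaccination dose 1".
- **Step 2** begins "The QALY/week for the 7 days post dose is calculated for each subject using the following formula". The formula is labelled AUC 0-7 but runs from k = 1 to 6. Below it, t(k) is the day of assessment k, whereas Y(k) is the score on study day k.
- **Step 3** takes baseline minus area, with no adjustment for length.

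The text around these steps disagrees about the window. Pointing to seven days, Step 3 says "Because the AUC must be calculated over a period of 7 days, the day 8 value cannot be included in the formula", Table 5 starts at day 0, and Protocol 10.5 sums from 0 to 6, although it labels the result AUC 0-6. Pointing to day 1 as the start, the opening of 7.1.3.4 speaks of "QALY loss over the 7 days (day 1 to day 7) post dose 1 and dose 2", and the endpoint in SAP 4.2 is baseline "versus combined score over the period day 1 to day 7". Day 1 to day 7 holds seven assessments but only six one-day intervals.

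Below Table 5 the SAP concludes: "The AUC between days 0 and 7 is 4.475. Hence the QALY loss / week is calculated as 1.534".

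**The concern.** A loss formed as baseline minus area is zero for an unchanged subject only if both terms cover the same length of time. Here one term covers seven days and the other, as written, covers six. The missing day is then counted as lost health.

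QALY change is a secondary endpoint, but its absolute level is what the study needs. Protocol 1.2.2 says it will be compared with the loss from zoster and postherpetic neuralgia, and Protocol 1.2.1 says it will enter net-QALY models. A false loss in every subject with complete data shifts that level directly.

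The false loss also scales with utility, so it does not cancel between subgroups. If non-frail subjects sat at a flat 1.0 and frail subjects at a flat 0.8 (assumed values), the frailty contrast in the planned regression would gain a spurious 0.2 utility-days.

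The example in Table 5, which should show a programmer which reading is meant, contains errors of its own.

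**Working it through.** **Inputs (SAP Table 5, hypothetical subject).** Utilities: day -7 0.89, day 0 0.85, day 1 0.75, day 2 0.70, day 3 0.72, day 4 0.74, day 5 0.75, day 7 0.78 (interpolated), day 8 0.80. Comparator: 3.65 days, equal to 0.01 QALY, for a zoster case without postherpetic neuralgia (Protocol 1.2.1).

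**Formula.** Area = sum of (t(k+1) - t(k)) × (Y(k) + Y(k+1))/2. Loss = baseline - area.

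**1. Reproducing the printed figures.**
- Baseline: 7 × (0.89 + 0.85)/2 = 7 × 0.87 = 6.09. This agrees.
- Area: 0.800 + 0.725 + 0.710 + 0.730 + 0.745 + 0.765 = 4.475. This agrees, but the last product (day 5 to day 7) uses width 1 for a two-day interval. A width of 2 is printed on the day 7 row and enters no product.
- Loss: 6.09 - 4.475 = 1.615. The SAP prints 1.534, which would need an area of 4.556.

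**2. The same subject with true widths.**
- Days 0 to 7: 0.800 + 0.725 + 0.710 + 0.730 + 0.745 + 2 × 0.765 = 5.240.
- Days 1 to 7: 5.240 - 0.800 = 4.440.
- Six-day baseline: 6 × 0.87 = 5.22.

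| Calculation | Baseline | Area | Loss |
|---|---|---|---|
| Table 5 as printed | 6.09 | 4.475 | 1.534 (1.615 by subtraction) |
| Step 2 with k as study day (days 1 to 7), 7-day baseline | 6.09 | 4.440 | 1.650 |
| Days 0 to 7, 7-day baseline | 6.09 | 5.240 | 0.850 |
| Days 1 to 7, 6-day baseline | 5.22 | 4.440 | 0.780 |

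Using the unrounded day 7 value (0.7833) changes 0.850 to 0.847. None of these calculations gives 1.534.

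**3. Size of the excess under Step 2 as written.**
- *k as study day.* The area covers days 1 to 7. The excess over a days 0 to 7 calculation is the dropped first trapezoid, (Y0 + Y1)/2. In the example this is (0.85 + 0.75)/2 = 0.800 = 1.650 - 0.850, and 0.80/3.65 = 22%. Against the matched days 1 to 7 version it is 1.650 - 0.780 = 0.870, and 0.87/3.65 = 24%.
- *k as assessment number, k = 1 at day 0, complete daily data.* The area stops at day 6 and the excess is (Y6 + Y7)/2. Filling in day 6 by the same interpolation (0.7667, with day 7 at 0.7833), the days 0 to 6 loss is 1.622 against 0.847. The excess is 0.775, and 0.775/3.65 = 21%.
- *Flat utility u, complete data.* Both readings give 7u - 6u = u. At u = 0.80 this is 0.80/3.65 = 22%; at u = 1.00 it is 1.00/3.65 = 27%. The range of u is assumed. Over two doses the false loss is 1.60 to 2.00 utility-days.

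**4. Unit.** These losses are in utility-days. By the protocol's own conversion, 0.850/365 = 0.0023 QALY.

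**The case against.** The best defence is that the intended calculation can be recovered. The AUC 0-7 label, the statement that the area must span seven days, Table 5's day 0 row and Protocol 10.5 all point to days 0 to 7, so a mis-set summation limit is the likelier explanation. A programmer who follows Table 5 includes the day 0 to day 1 trapezoid. On the study-day reading, a line-by-line check against the table would expose that row as missing. Step 3 also computes the area however many assessments there are. If k counts assessments from day 0, the example subject, who has no day 6, has exactly seven usable points; six terms with true widths then reach day 7 and give 5.240 and 0.850.

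These points stand, and they limit the claim: the bias depends on how Step 2 is programmed. They do not remove it. On the assessment-number reading, a subject with complete daily data still loses the last day, and the SAP expects most subjects to have complete data. The example cannot show this, because its subject lacks day 6. Following Table 5 means setting aside the written formula for a table with two errors; copying its width-1 step would shrink that subject's area by 0.765.

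It is also true that the endpoint is secondary, the analyses are descriptive, and the documents cannot show whether any program contained the error. That bears on how far the problem reaches. The specification still does not determine the result.

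**Conclusion.** The concern holds. SAP 7.1.3.4 is inconsistent about its window. Followed as written with complete daily data, Step 2 overstates QALY loss by about one day of utility per dose. At assumed utilities of 0.80 to 1.00 that is 0.80 to 1.00 utility-days, or 22% to 27% of the loss the protocol cites for a zoster case without postherpetic neuralgia. In the SAP's own example the excess is 0.775 to 0.87, depending on the index reading and the corrected version used for comparison. There is no such bias if the program follows the days 0 to 7 text with true widths.

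Separately, and without any assumption, Table 5 is wrong. Its printed loss of 1.534 disagrees with its own subtraction and is about 1.8 times the days 0 to 7 value of 0.850 (1.534/0.850).

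The primary SF-36 Physical Functioning endpoint is not touched. The derivation must be corrected before any QALY result is used.

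**What to change.** Give the baseline and the area the same span, and define k once for both t and Y. Either version below is consistent.

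- **Preferred, in line with Protocol 10.5 and the AUC 0-7 label:** sum k = 0 to 6 from the pre-vaccination score on the day of vaccination (day 0 for dose 1, day 60 for dose 2) to day 7, with actual interval widths, against 7 × mean baseline. State that the vaccination-day score enters both the area and the baseline although the endpoint is worded as day 1 to day 7. Relabel the protocol's AUC 0-6, since its last term reaches day 7.
- **Alternative, closer to the endpoint wording:** keep the day 1 to day 7 area and use 6 × mean baseline.

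With either version:

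- Correct Table 5. For days 0 to 7: last width 2, last product 1.530, area 5.240, loss 0.850. For days 1 to 7: area 4.440, baseline 5.220, loss 0.780.
- Add a second example with complete daily scores and constant utility, for which the loss must be zero.
- State that the result is in utility-days, and divide by 365 before calling it a QALY.
- Say what happens when a subject has no assessment on or after day 7, since a shortened area would again be set against a full baseline.

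The cost is SAP wording, a corrected table, one protocol label and a small change to the area calculation. The daily scores are already collected, so there is no data or patient cost.

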### Step3

The QALY Loss is then calculated as the difference between the baseline utility (from step 1) and the AUC value (from step 2).

It is anticipated that the majority of subjects will have daily assessments post dose according to the schedule (i.e. on each of the days 1 to 7) however it is expected that some subjects will be missing daily assessments post dose. In the case of missing assessments between days 1 and 7 the AUC in step 2 will be calculated regardless of the number of assessments post dose. However in the case of the last assessment falling outside of the 7 day window, (for example on day 8), an adjustment will be made before calculating the AUC.

[Figure 1](#) represents the Utility scores for a hypothetical subject. This subject has consecutive assessments on day 5 and day 8 and no assessments on days 6 or 7. Because the AUC must be calculated over a period of 7 days, the day 8 value cannot be included in the formula. However to calculate the AUC, a derived value on day 7 is calculated based on a linear interpolation of the values on days 5 and 8. This derived value on day 7 is then included in the formula given in step 2. The dashed line in the figure represents the linear interpolation between the two assessments either side of day 7.

The calculation of the QALY loss for this hypothetical subject is explained in [Table 5](#).

[figure not shown]

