10.5. Derived and transformed data

The calculation of the QALY will be based on the EQ-5D questionnaire. The EQ-5D is a generic measure of health status that provides a simple description profile based on the following 5 items: mobility, self-care, usual activities, pain/discomfort and anxiety/depression.

For each day, the combination of the scores recorded in each of these 5 items, will be transformed in a single index value.

The QALY/week is calculated for each subject using the following formula:

$$AUC_{0-6} = \sum_{(0 \text{ to } 6)} (t_{k+1} - t_k) * (Y_k + Y_{k+1}) / 2$$

where Y_k is the score at day k and t is time at day k.

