## 7.1.3. Quality of Life data

### 7.1.3.1. Calculation of study day for SF-36 and EQ-5D Assessments

Each EQ-5D and SF-36 assessment at a scheduled time point will be re-classified into time points based on the date of assessment relative to date of vaccination:

Studyday=date of assessment – date of vaccination.

To be considered evaluable at day 0 a questionnaire must have been filled in within 14 days of vaccination date. Questionnaires without a date of assessment were to be considered not evaluable. In case of two questionnaires with the same date of assessment the minimum value (i.e. the value which represents worst quality of life) of the two assessments will be selected as evaluable.

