## 7.2.3. Quality of Life data

At dose 1, if one of the Day -7 or Day 0 pre-vaccination assessments is missing, the baseline value will simply be the non-missing assessment. At dose 2, if 2 or more of the 3 pre-vaccination assessments are missing, the baseline value will be considered missing.

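### QALY loss subtracts an AUC that may cover fewer than 7 days from a fixed 7-day baseline, so the loss is overstated

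*SAP*

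**What the plan says.** SAP 7.1.3.4 builds the QALY loss in three steps.

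- **Step 1, baseline.** The mean of the pre-vaccination utilities is multiplied by 7. For dose 1 the mean is over Day -7 and Day 0: "This value will then be assumed to have been the utility in the 7 days pre vaccination dose 1". Dose 2 adds Day 60.
- **Step 2, AUC.** "The QALY/week for the 7 days post dose is calculated for each subject using the following formula": a trapezoidal sum labelled AUC0-7 with the index k running from 1 to 6. The section's opening says the method is used "in order to estimate the QALY loss over the 7 days (day 1 to day 7) post dose 1 and dose 2".
- **Step 3, difference.** The AUC is subtracted from the Step 1 value, with no adjustment for the time actually covered.

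Protocol 10.5 also states that "The QALY/week is calculated for each subject using the following formula", but its sum runs from 0 to 6 and is labelled AUC0-6.

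On incomplete records, Step 3 says that with "missing assessments between days 1 and 7 the AUC in step 2 will be calculated regardless of the number of assessments post dose". The one adjustment it describes is for a last form later than Day 7, where a Day 7 value is interpolated. The reason given is: "Because the AUC must be calculated over a period of 7 days, the day 8 value cannot be included in the formula". SAP 7.2.3 deals only with missing baseline forms; at dose 1, "if one of the Day -7 or Day 0 pre-vaccination assessments is missing, the baseline value will simply be the non-missing assessment". SAP 7.1.3.1 adds: "Questionnaires without a date of assessment were to be considered not evaluable".

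Table 5 works through a hypothetical subject and reports an AUC of 4.475 and a loss of 1.534 against a baseline of 6.09. SAP 6.2.3 plans a sensitivity analysis restricted to subjects with valid forms on at least 4 of the 7 days after each dose.

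**The concern.** A 7-day baseline minus an AUC is a loss only if the AUC also covers 7 days. The SAP accepts this principle but leaves two ways for the AUC to be shorter.

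**(A) Records that end early.** If the on-site Visit 3 or Visit 5 form is missing, or is undated and therefore not evaluable, the last usable form precedes Day 7. No rule covers this. If the area is summed over the forms available, as Table 5 does, the days after the last form add no area but are still charged against the baseline. Each is in effect scored as zero utility. Gaps between two forms are not part of the problem, because the trapezoid bridges them.

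**(B) The printed sum.** Six one-day terms cannot cover Days 0 to 7. If k is the study day they cover Days 1-7; if k counts forms starting at Day 0 they cover Days 0-6. Both are 6 days.

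**(C) The worked example.** Table 5 should settle which method is meant, but its own arithmetic does not hold.

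With positive utilities, (A) and (B) both push the loss upward. QALY change is a secondary endpoint, and Protocol 1.2.1 and 1.2.2 say the result will enter net-QALY models and be compared with the loss from HZ and PHN.

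**Working it through.** **Inputs (SAP Table 5).** Utilities: Day -7 0.89; Day 0 0.85; Day 1 0.75; Day 2 0.70; Day 3 0.72; Day 4 0.74; Day 5 0.75; Day 7 0.78 (interpolated between Day 5 and a Day 8 value of 0.80). Baseline = 7 × (0.89 + 0.85)/2 = 7 × 0.87 = 6.09.

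**The plan's own figure.** The printed products are 0.800 + 0.725 + 0.710 + 0.730 + 0.745 + 0.765 = 4.475. The last term is the Day 5-7 mean multiplied by 1, although the interval is 2 days long. The loss would then be 6.09 − 4.475 = 1.615, not the printed 1.534, which would need an AUC of 6.09 − 1.534 = 4.556. Starting at Day 1, using only one baseline value, leaving the Day 7 value unrounded (0.7833) or including Day 8 does not give a loss of 1.534 either. The number does equal 2 × 0.767, the Day 5-7 area with the unrounded Day 7 value, so it may have been copied from the wrong cell; that is a guess.

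**Correct widths.** Day 0-5 area = 0.800 + 0.725 + 0.710 + 0.730 + 0.745 = 3.710. Day 5-7 area = 2 × 0.765 = 1.530. AUC = 5.240 and loss = 6.09 − 5.240 = 0.850.

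**(A) Same subject, Day 8 form missing or undated, so the last form is Day 5.**

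| Start of curve | AUC, full span | Loss | AUC, stops Day 5 | Loss | Ratio |
|---|---|---|---|---|---|
| Day 0 | 5.240 | 0.850 | 3.710 | 2.380 | 2.80 |
| Day 1 (drop 0.800) | 4.440 | 1.650 | 2.910 | 3.180 | 1.93 |

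The excess is 1.530 days on either reading, which is exactly the missing Day 5-7 area.

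**Effect of (A) on the mean.** Shift = proportion affected × trailing days × utility. With utility 0.85 and assumed proportions:

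- 1% × 1 day × 0.85 = 0.0085
- 5% × 1 day × 0.85 = 0.0425
- 5% × 3 days × 0.85 = 0.1275
- 10% × 3 days × 0.85 = 0.255

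Against the 3.65 days that Protocol 1.2.1 cites for an HZ case without PHN, the extremes are 0.0085/3.65 = 0.2% and 0.255/3.65 = 7.0%.

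**The 4-of-7 sensitivity analysis.** Four valid days with the last before Day 7 means that the last form is on Day 4 or later. The analysis therefore limits the artefact to three trailing days but keeps a Days 1-4 record. The main analysis has no such limit.

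**(B) Six-term sum, complete record, constant utility u, true loss 0.** Loss = 7u − 6u = u. This is 0.85 days per dose at u = 0.85, and 0.75 to 1.00 for u from 0.75 to 1.00. With the seven terms of Protocol 10.5 it is 7u − 7u = 0.

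**Does the choice of repair matter?** For the Table 5 subject with a Day 0 start:

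| Last form | Carry last value to Day 7 | Baseline matched to observed span |
|---|---|---|
| Day 5 | 6.09 − (3.710 + 2 × 0.75) = 0.880 | 5 × 0.87 − 3.710 = 0.640 |
| Day 3 (area 2.235) | 6.09 − (2.235 + 4 × 0.72) = 0.975 | 3 × 0.87 − 2.235 = 0.375 |

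It does, so the rule has to be fixed before the data are seen.

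**The case against.** - **Part (A) is silence, not an instruction to score zero.** The SAP says the AUC must span 7 days, and with k as the study day the sum is undefined without a Day 7 value, so a programmer might set the result to missing. This stands in part: zero utility is one implementation. But setting the result to missing sits badly with computing the AUC whatever the number of forms, and the 7-day sentence comes with a remedy only for late forms.
- **The trigger should be rare.** Protocol Table 6 puts Visits 3 and 5 at 7-10 days after each dose, so an in-window form falls on Day 7 or is interpolated back to it. Home forms are returned at those visits (Protocol 5.5.2.11), so a missed visit may remove the whole set. This stands, and the low end of the assumed range is the more likely.
- **The 3.65-day comparison mixes units.** That figure is per HZ case; the shift is per vaccinated subject per dose. This stands: the percentages give scale only.
- **Part (B) is probably an index slip.** The AUC0-7 label, Table 5's Day 0 start and the protocol's seven terms all point to a full week, and SAP Section 9 declares no change. As to intent this is likely right. But the opening of 7.1.3.4 says Day 1 to Day 7, which supports the literal sum.
- **Table 5 does print a width of 2, on the Day 7 row.** True, and it suggests misaligned rows. The product and the total nevertheless use 1.
- **The endpoint is secondary, with no success criterion (Protocol 10.7).** This stands and limits the consequence.

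**Conclusion.** The concern holds. As written, the plan does not keep the AUC and the baseline on the same time span, contrary to its own 7-day requirement, and the departures overstate QALY loss.

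For a subject whose forms stop early, summing over the available forms adds about one day of utility per trailing day: 1.530 days for the Table 5 subject stopping at Day 5. The effect on the mean is about 0.009 to 0.26 days per dose. That range rests on assumed proportions of 1-10%, 1-3 trailing days and utility 0.85; the documents give no rate of missing Day 7 forms, and the true share is probably small. The six-term sum, if programmed literally, would matter more: about 0.85 days of false loss in every complete record. If the programmer uses the protocol's seven terms, that part is nil.

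The textual inconsistency and the Table 5 errors are certain; the size in practice is not. The primary SF-36 PF endpoint is not affected. This should be corrected before QALY loss is computed.

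**What to change.** 1. Define the curve from Day 0 to Day 7 with seven daily intervals. Align the opening of SAP 7.1.3.4 and the Step 2 index with Protocol 10.5 and Table 5, and change the protocol's AUC0-6 label to match.
2. Pre-specify one rule for a last evaluable form before Day 7 that puts the AUC and the baseline on the same span. One option is to carry the last utility to Day 7, with a baseline matched to the observed span as sensitivity analysis. Treat subjects with no post-dose form as missing.
3. Apply the same rule in the SAP 6.2.3 sensitivity analysis.
4. Correct Table 5: Day 5-7 width 2, AUC 5.240, loss 0.850.

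The cost is a few lines of SAP text and a small program change. The downside is that a few values are extrapolated: carry-forward may prolong early symptoms and overstate the loss, while a matched span may understate it. Reporting both shows how much the choice matters.
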